10.5 Analysis Data Sets

Data will be combined into analysis data sets in a form similar to the CDISC ADaM structure, from which all outputs will be generated. It is anticipated there will be the regular subject level data set (similar to ADSL), an efficacy data set (similar to ADEF), a laboratory data set (similar to ADLB), an adverse events data set (similar to ADAE), and perhaps others.

10.6 Description of Statistical Methods

1. Adjustment for non-normality:

- a. The primary endpoint analysis is based on the mean pad weight reduction per hour as a percent having a normal distribution. Values will be checked for normality via the Kolmogorov Smirnov test, and a transformation may be needed prior to the analysis. First the percent change from baseline will be examined, and if the data are not normally distributed then a log transform of the ratio of the post-treatment result to the post-control will be utilized. The standard error of this logged quantity and resulting lower bound of the 1- (adjusted alpha) confidence interval will be determined. Then this lower bound will be exponentiated to get the ratio in the original data units. 100 times this value can now be interpreted as the percent of the post-treatment result that is left from the baseline. This is because the post-treatment result will be less than the post-control result. Subtracting this result from 100% will give the lowest percentage value needed to achieve statistical significance. If this lower bound is greater than 50% and the raw percent change from baseline is greater than this result then the primary endpoint has been reached.

The expected results suggest that the percent change from baseline should be normal, thus validating the sample size and power calculations. Since those assumptions are conservative it is felt that any transformation of the data and subsequent modification of the analysis (e.g., see adjustment for site below) still allow for this endpoint to have sufficient power.

b. Secondary Endpoints:

- i. Should the difference in SUI episodes be non-normal then the natural log of the baseline and treatment phase scores will be taken and the natural log of the ratio of the post-treatment result to that of the baseline will be analyzed in the same fashion as described in “a” above. A raw difference of 0 would translate to a ratio of 1.0 after exponentiation back. Since the difference is expected to be negative, the upper bound of the raw (transformed back) is compared to 1. If it is less than the endpoint has been reached, indicating that the treatment mean is statistically significantly less than the control mean.
- ii. If the scores of the QOL indicate a significant difference from normality then a natural log transformation will be done and modeled

2. For the other secondary analysis (safety outcomes examination) descriptive and possibly narrative results will be presented. For the exploratory outcomes of comfort and successful usage results will be reported similarly. Details will appear in the SAP.

Results for the primary and secondary endpoints will be presented in tables, with continuous data exhibited via descriptive summaries (n, mean (std), median, min, max); n will be a whole number, means, medians, and minimum and maximum values will have one decimal place, and standard deviation will have two. Categorical measures (counts) reported as n (%), with n being a whole number and the percent having one decimal place.

As mentioned above, the analyses for the primary and two secondary endpoints will be done on the mITT population and no imputation should be necessary. For the primary endpoint and the SUI episodes secondary endpoint, by definition, the subject must have participated on one day of the treatment period; therefore, there will be a pad weight gain per hour measure and (conceivably) a diary entry for the number of SUI episodes; both of these would be the values for analysis for that subject. If they are not retrievable then they are missing. If a withdrawing mITT subject is able to complete the quality of life questionnaire that data would be used; if not that subject has a missing value for the post-treatment QOL score. Should participants withdraw replacements will be utilized until 50 per protocol participants have completed the study. Possible screening for as many as 80 participants should provide this needed sample size. No covariate use is planned for any analysis.

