10.3 Sample Size and Study Outcome Determination

A precision approach will be used to determine the appropriate sample size and power for the study. For power and sample size considerations a type 1 error rate (alpha) of 0.05, one-sided, will be used. Given a sample size of 50 the calculations have been done with various standard deviations to show power below and above 90% (see Table 1 below). Sixty to seventy participants will be enrolled to allow for the fifty per-protocol participants, although the analyses will be done on the mITT population.

The assumptions made for the power and sample size computations come from the Poise study (Ziv et al), where their assumption for the effect size was reduction in pad weight gain per 8 hours of 70%, with a standard deviation of 15%. The results of the study showed an 86% reduction in pad weight gain per 8 hours with a 9% standard deviation. Given those results, this study's assumptions of 60% improvement and a range of standard deviations from 15% to 20% appear conservative; thus, the expected results would indicate a successful outcome for the primary endpoint.

The computations below are based on the precision method, which in the case of this study computes a lower 95% confidence limit for the percentage change. Here we consider a changes around 60% in the explanation of the table. Different standard deviations are used with the sample size of 50.

Table 1.

n	½ width of CI	Std Dev	Power
50	5	16	0.999
50	5	17	0.991
50	5	18	0.956
50	5	19	0.869
50	5	20	0.720
50	6	20	0.995

The first entry in the table shows that if the resulting mean reduction in pad weight gain was 60% and the standard deviation of the mean percentage change was 16%, the lower limit of the 95% confidence interval for 60% would be 55%: 60% - 5% (½ width), with 99.9% probability (power). The last line in the table above shows that the resulting mean percentage change would have to be greater than 56 for the power to be 99.5% (56% - 6% ½ width = 50%, not greater than 50%) if the standard deviation was 20%. If the result was 60% the lower limit of the confidence interval would be 54%: (60% - 6%) with 99.5% power. Thus, for all lines above except 4 and 5 the endpoint was reached with greater than 90% power.

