10.4 Statistical Hypotheses and Data Description

1. Type 1 Error and Multiplicity Concerns:

The inferential tests for the one primary and two secondary endpoints were initially conceived to be one-sided using alpha=0.05. Since the sponsor wishes to use the success of all three for labeling and marketing purposes, a Bonferroni adjustment for multiple comparisons will be employed. Thus, statistical significance will be indicated for each endpoint if the p-value is less than 0.0167.

2. Primary Endpoint:

There is one primary endpoint, for efficacy. The objective is to show that reduction in the mean pad weight gain per hour is >50% in the treatment period. Thus, the null hypothesis is that the mean weight gain reduction per hour is <=50%, and the alternative is that it is >50%, from the control period (no device) to the treatment period (women wearing the device). The data values will be computed for each woman as:

[(total weight of all pads worn during the treatment period/hrs. pads are worn during treatment)

minus

(total weight of all pads worn during the control period/ hrs. pads are worn during control)]

The above quantity divided by
(total weight of all pads worn during the control period/ hrs. pads are worn during control)

This resulting quantity is then multiplied by 100.

Ex. Subject's total pad weight for control period is 140 grams. Pads were worn for a total of 100 hours. Weight/hr. is $140/100 = 1.4$ g/hr. Subject's total pad weight for treatment period is 60 grams. Subject wore pads for 100 hours. Pad weight per hour is $60/100 = 0.6$ g/hr. Difference, treatment – control is $0.6 - 1.4 = -0.8$ g/hr. For the percent change, $100 * (-0.8/1.4) = -57.143\%$. Therefore the reduction in pad weight gain is 57.143%.

The null hypothesis will be that the mean reduction in pad weight gain per hour is less than or equal to 50%, with the alternative that it is greater than 50%. If the raw percentage change data appear to be normally distributed, a paired t-test will be used to test the hypothesis. If not, see section 10.6 (2).

The precision method will be utilized to determine success. The precision approach creates a lower bound for a confidence interval that is higher than the reference, in this case 50%. This 50% standard was chosen based on the FDA guidance document.

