- b. For the quality of life score there will be three measures as described in the visit schedule above. For descriptive purposes the results and change from the previous visit will be shown, as well as the change from the enrollment visit to the post-treatment visit. The changes will likely be negative scores as the QOL is expected to improve, as the instrument records lower numbers as indicating a better quality of life. For the purposes of inferential analysis, a mixed model analysis of variance on the scores will be used on the result at time t (t=baseline, post-control, post-treatment) with time as a fixed effect and subject as a random effect. Thus, the null hypothesis is that there is no significant difference from baseline/enrollment to post-treatment, i.e., that the mean change in score is 0. The alternative is that this change is less than 0. Correlation of scores within subjects will be considered as compound symmetric. The p-value indicating the significance of the least square mean score at the third time-point compared to that at the first time-point will determine if the endpoint is met.

All inferential testing will be done on the mITT population and will be one-sided. As noted above statistical significance will be reached if the relevant p-value is less than 0.0167. Results for all populations will be reported.

There is a secondary safety endpoint as described earlier in the protocol. Safety reporting using urinalysis, vaginal swab, vaginal examination, and evaluation will be descriptive and narrative in nature.

Similarly, exploratory endpoint results of comfort and successful use will be descriptive. No inferential hypotheses will be used here.

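### If the normality check fails, the primary analysis moves from the arithmetic to the geometric mean reduction at the same 50% bar, undeclared, and its bound is described in the wrong direction

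*Combined protocol and SAP*

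**What the plan says.** Section 10.4(2) computes one percent change per woman (treatment rate minus control rate, divided by control rate) and sets the hypothesis on the mean: "The null hypothesis will be that the mean reduction in pad weight gain per hour is less than or equal to 50"%. The test follows from the look of the data: "If the raw percentage change data appear to be normally distributed, a paired t-test will be used to test the hypothesis". Otherwise the reader is sent to section 10.6(2), although the relevant text is in 10.6(1)(a).

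That text says: "Values will be checked for normality via the Kolmogorov Smirnov test". It gives no significance level and no version of the test. If the data fail, "if the data are not normally distributed then a log transform of the ratio of the post-treatment result to the post-control will be utilized". The lower bound of the logged quantity is then exponentiated, multiplied by 100 and subtracted from 100%. The endpoint is met if the result exceeds 50% and the raw percent change exceeds that result.

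On error rate, 10.4(1) says that "statistical significance will be indicated for each endpoint if the p-value is less than 0.0167", and 10.4(3) that "All inferential testing will be done on the mITT population and will be one-sided". Neither section says that the log analysis addresses a different quantity.

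**The concern.** The null hypothesis concerns an arithmetic mean. A mean of logs, exponentiated, is a geometric mean. For ratios of treatment to control the geometric mean is never above the arithmetic mean, so the geometric reduction is never below the arithmetic one. Keeping 50% as the bar therefore makes the fallback an easier hypothesis, and the data choose which hypothesis is tested. Skewness both triggers the switch and widens the gap between the two quantities.

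The direction of the bound is a second fault in the same text. A lower bound for the ratio becomes an upper limit for the reduction once it is subtracted from 100%, yet the plan calls it the lower bound. The same section gets the direction right for SUI episodes, where the upper bound is compared with 1.

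At stake is the sole primary success decision, which the sponsor wants to use for labelling.

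**Working it through.** **Inputs from the plan.** n = 50; null mean reduction 50%; assumed effect 60% with SD 15-20% (10.3); one-sided alpha 0.05/3 = 0.0167 (10.4). **Assumed, not in the plan:** K-S with estimated mean and SD at level 0.05; the distribution of the ratios; SDs outside 15-20%.

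**1. The plan's own figures.** For Table 1, 10.3 states that "a type 1 error rate (alpha) of 0.05, one-sided, will be used". The probability that the half-width is at most w is P(χ²₄₉ ≤ 49·50·(w/(t·SD))²) with t = t(0.95, 49) = 1.677. For SD 16 and w = 5 the bound is 2450 × (5/26.83)² = 85.1, which gives 0.9989. Conditional on the interval covering the true mean, the six rows are 0.9989, 0.9906, 0.9560, 0.8687, 0.7205 and 0.9951. The plan prints 0.999, 0.991, 0.956, 0.869, 0.720 and 0.995. Table 1 is thus reproduced as a normal-theory calculation for the arithmetic mean percent change. It says nothing about the log branch.

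**2. The two targets.** Let R be a woman's ratio of treatment to control rate.
- t-test branch: 100 × (1 − mean R)
- log branch: 100 × (1 − exp(mean ln R))

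For lognormal R with mean 0.5, the geometric mean ratio is 0.5/√(1 + (SD/0.5)²). At SD 15% it is 0.5/√1.09 = 0.479, a reduction of 52.1%. At SD 20% it is 0.5/√1.16 = 0.464, a reduction of 53.6%. SD 30% and 40% give 57.1% and 61.0%. A device exactly at the stated null is already above the bar in the log branch.

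**3. The rule as printed.** Let m and s be the mean and SD of ln R. The lower bound is m − t·s/√n, where t is now the quantile for 0.0167. Then exp(m − t·s/√n) ≤ exp(m) ≤ mean R, so 100 × (1 − exp(m − t·s/√n)) is at least the raw mean reduction. The second condition requires the raw mean reduction to exceed this quantity, which is impossible. Every trial that switches fails. Simulated with lognormal ratios:
- true reduction 50%: overall success about 1-2%
- true reduction 60%, SD 12%: success about 65%, against 99.8% for the t-test
- true reduction 60%, SD 17%: success about 46%, against 95%

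**4. The rule as evidently intended.** The limit is 100 × (1 − exp(m + t·s/√n)). Success in the log branch needs this limit above 50% and the raw mean reduction above the limit. Simulated at a true mean reduction of 50%, lognormal ratios, whole two-stage rule with both conditions:

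| SD of percent change | Success, two-stage | Success, t-test alone |
|---|---|---|
| 15% | 6.1% | 2.7% |
| 20% | 12.3% | 3.1% |
| 26.6% | 24.9% | 3.6% |
| 30% | 31.0% | 4.0-4.1% |
| 32.9% | 30.4% | 4.4% |
| 40% | 14.2% | 5.1-5.2% |

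The nominal rate is 1.67%. The switch occurs in about 33% of trials at SD 15.3% and 53% at SD 20.8%. The raw-change condition practically never binds at SD 15-21%. At SD 40% it cuts success from 58% to 14%.

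**5. Sensitivity of step 4 to the assumptions.**
- Normal data, SD 16%: 2.1%.
- Symmetric beta data, SD 15-20%: 2.2-2.9%.
- Gamma ratios: 8.1% at SD 20%, 19.2% at SD 30%.
- A mixture with 80% of women at mean ratio 0.375 and 20% at 1.0 (SD about 30%): 41%.
- Lognormal ratios with ordinary K-S critical values, not adjusted for estimated parameters: the switch occurs in only 1-4% of trials at SD 15-21%, and success is 2.9-3.8%. At SD 27-33% success is 7-9%.

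**The case against.** The strongest reply has four parts.

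- **The printed rule is not lenient.** Correct. Taken literally, the rule makes the log branch fail every time, and overall error at the null is near nominal. A reader might infer that the text as it stands inflates type I error. It does not; inflation appears only when the bound is taken from the side the plan evidently means. But the literal rule costs heavily in power, and correcting the direction alone, the obvious repair, brings in the inflation.
- **The raw-change condition protects the trial.** In part. A reader might infer that the trial could succeed with an observed mean reduction of 50% or less. In the log branch it cannot, because the raw mean must exceed a limit that itself exceeds 50%. The concern is the true mean. The condition does not control error at the plan's SDs, where it does not bind. It does mean that inflation falls again at large SD, so it should not be described as growing steadily with skewness.
- **The plan expects normal percent changes.** If that holds, error is about 2%. But the fallback exists for the case where it does not hold, and the reassurance in 10.6(1a) is about power, not type I error.
- **Section 10.2 defers detail to a later SAP.** The K-S level and version could be settled there. The quantity tested, the 50% bar and the direction of the bound are already fixed in 10.6.

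**Conclusion.** The concern holds as a change of target that the plan does not declare, in a fallback that is wrong under either reading. Read literally, the log branch can never be passed, even by an effective device. Read as intended, type I error for the stated null is inflated when the ratios are skewed. At the plan's own SDs of 15-20% it is about 6-12%, roughly four to seven times 1.67%. It is about 25-31% at SD 27-33%, outside the plan's range, and about 14% at SD 40%.

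These sizes rest on n = 50 (the mITT set may be larger), lognormal ratios, and K-S with estimated parameters at 0.05. The documents give neither the ratio distribution nor the K-S level and version. A claim that error is far above nominal whatever the data is therefore not supported: near-normal data or ordinary K-S critical values leave it at about 2-4% for SDs of roughly 15-21%. That so much depends on an unspecified check is itself a reason not to let the check choose the primary analysis.

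**What to change.** In 10.4(2) and 10.6(1a), delete the normality check as a switch. Fix one primary analysis: the mean per-woman percent reduction against 50%, with a one-sided lower limit at 0.0167, whatever the distribution.

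- **Preferred limit:** bootstrap-t, with error of about 2% at SD 15-27% under lognormal ratios.
- **Acceptable:** the one-sample t-test, which runs at about 3-4% with skewed data over that range.
- **Possible alternative:** a lognormal interval aimed at the arithmetic mean (log-mean plus half the log-variance), with error of 2.1-2.4% at SD 15-30%. It relies on the lognormal shape.

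Report the log-ratio result only as a sensitivity analysis, labelled as a geometric-mean reduction and using the upper bound of the log ratio. Correct the cross-reference in 10.4(2), and remove the log-ratio option for the primary outcome in 10.7.

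The cost is wording, provided it is done before data are seen. The downside is that with skewed data the endpoint is harder to meet than under the intended switch.

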A successful outcome for this endpoint would be any result where the lower limit of the 95% confidence interval is above 50% with more than 90% power, as explained above. When the results are tabulated, another table will be created with the n's and standard deviations from the study for comparison to the study results.

Also, this sample size should also be sufficient for inferential analysis of the secondary endpoints.

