Power and sample size calculations determine scenarios of success. When the resulting mean reduction in pad weight gain per hour is quantified, its lower limit of a $(1-0.0167)\%$ confidence level is determined. This value is then compared to parameters determined to be efficacious in the sample size calculations (section 10.3). It is expected that the mean reduction per hour will be >50% such that the lower limit of the confidence interval for that result will be higher than 50% with adequate power to suggest success for the study.

3. Secondary Endpoints:

- a. For the change in SUI episodes endpoint each subject will have a change in the number of episodes per day from the control period to the treatment period. Specifically, the number of episodes will be recorded each day in the diary. For the control phase, there will be (at most) 7 days of data. The mean number of SUI episodes per day will be computed for each subject. The same measures

will occur in the treatment period for the analysis period, the last 7 days. Each subject will again have a mean number of SUI episodes per day. If the pads are not worn for the entire time specified during a day, the fraction of the day the pads are worn will be used in computing the number of days. Therefore, there will be, say, 50 differences comprised of mean number of SUI episodes per day in the treatment period minus mean number of SUI episodes per day for control period. (These numbers will likely be negative.) The mean of these 50 mean differences represents the mean change in the number of SUI episodes per day from the control period to the treatment period. The null hypothesis will then be that the mean change in the number of SUI episodes is 0, and the alternative is that it is less than 0, analyzed using a paired t-test. A p-value of less than 0.0167 indicates success.

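### If the normality check fails, the primary fallback in section 10.6 tests the upper, not the lower, limit of the reduction, and its second condition is undefined

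*Combined protocol and SAP*

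**What the plan says.** Section 10.4 sets the primary hypothesis on the mean of the per-woman percent reductions: "The null hypothesis will be that the mean reduction in pad weight gain per hour is less than or equal to 50" per cent. Success is described in the same direction in two places. Section 10.3 asks for "any result where the lower limit of the 95% confidence interval is above 50% with more than 90% power", and section 10.4 expects that "the lower limit of the confidence interval for that result will be higher than 50" per cent. After the Bonferroni adjustment the test is one-sided at 0.0167.

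Section 10.6 item 1.a applies only if a Kolmogorov-Smirnov check rejects normality. The analysis variable becomes the log of treatment over control. The plan finds the lower confidence limit of this quantity and continues: "Then this lower bound will be exponentiated to get the ratio in the original data units". One hundred times that value is described as the percentage left from baseline. Then: "Subtracting this result from 100% will give the lowest percentage value needed to achieve statistical significance". The decision rule begins "If this lower bound is greater than 50% and the raw percent change from baseline is greater than this result", and if both parts hold the endpoint is met.

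Item 1.b.i of the same section applies the same transformation to incontinence episodes, but there "the upper bound of the raw (transformed back) is compared to 1".

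Section 10.4 sends non-normal data to item 2 of section 10.6. The fallback is in item 1.

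**The concern.** The transformation from log ratio to percent reduction reverses order: the lower the ratio, the larger the reduction. The lower limit of the ratio is therefore the optimistic end of the interval for the reduction. A rule that asks whether that end exceeds 50% does not test the null hypothesis of section 10.4. It also conflicts with sections 10.3 and 10.4, and with item 1.b.i, which uses the correct side of the ratio.

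The second condition might have rescued the rule, but the phrase *this result* has at least three possible referents in the surrounding sentences, and each gives a different rule. At stake is the decision on the only primary endpoint, which section 10.4 says the sponsor wants for labeling, whenever the fallback is used.

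**Working it through.** **Inputs.** From the documents: n = 50, SD 15–20 points and an expected mean reduction of 60% (section 10.3); null value 50% and one-sided alpha 0.05/3 = 0.0167 (section 10.4). Hence t(0.9833, 49 df) = 2.189. Assumed, because the documents do not say: the shape of the data (normal, beta and log-normal are all shown) and a 0.05 level for the normality check.

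**The plan's own figures.** The worked example reproduces: 100 × (0.6 − 1.4)/1.4 = −57.143%. Table 1 reproduces from P(χ²₄₉ ≤ 49 × [h√50/(t × SD)]²) with h the half-width and one-sided alpha 0.05: 0.9989, 0.9909, 0.9573, 0.8719, 0.7260 and 0.9952, against the stated 0.999, 0.991, 0.956, 0.869, 0.720 and 0.995. Those inputs are sound. Table 1 does not address the fallback.

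**Direction of the limit.** Let d be the mean of ln(treatment/control), L = d − t × SE and U = d + t × SE. Since 100 × (1 − exp(x)) falls as x rises, L gives the upper limit of the reduction and U the lower. Example with geometric-mean ratio 0.40 and log-SD 0.385:

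- t × SE = 2.189 × 0.385/√50 = 0.119
- as written: 100 × (1 − 0.40 × exp(−0.119)) = 64.5%
- correct lower limit: 100 × (1 − 0.40 × exp(+0.119)) = 54.9%

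This step needs no distributional assumption.

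**The second condition, under three readings of *this result*.** The raw change is taken as the mean reduction, 100 × (1 − mean ratio).

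- (a) *The computed bound.* The arithmetic mean of the ratios is at least their geometric mean, so mean ratio ≥ exp(d) > exp(L). The mean reduction therefore always lies below the bound, and success is impossible.
- (b) *50%.* By the same inequality, a mean reduction above 50% already puts the bound above 50%. The rule reduces to an observed mean above 50%.
- (c) *The percentage remaining, 100 × exp(L).* In the example the mean reduction need only exceed 100 − 64.5 = 35.5%.

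**Fallback alone, true mean reduction exactly 50%.** Simulated pass rates are 0 under (a), about 50% under (b) and about 94–97% under (c), against 1.67%.

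**Whole procedure** (Kolmogorov-Smirnov check, then t limit or fallback):

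| | Normal or beta ratios | Log-normal ratios |
|---|---|---|
| True mean 50%: check fails | about 5–6% | 32–49% |
| False success, (a) | about 1.6% | about 2% |
| False success, (b) | 4–5% | 18–25% |
| False success, (c) | 6–8% | 32–48% |
| True mean 60%: success, t limit throughout | 90–99% | 86–98% |
| True mean 60%: success, (a) | 79–95% | 32–54% |

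**Would swapping the limit be enough?** At a true geometric-mean reduction of 50% (log-normal), using U rejects 1.62–1.65%, as intended. At a true arithmetic-mean reduction of 50%, which is the boundary of the section 10.4 null, it rejects about 10–21% across the three shapes. The t limit on the percent reductions rejects about 1.6–3.1% in the same cases.

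**The case against.** The intent is visible. Sections 10.3 and 10.4 state the right direction and item 1.b.i uses the right limit, so a careful programmer might correct the slip unprompted. Section 10.6 also expects normal data, in which case the fallback is entered in about 5% of trials. Both points stand and they limit the practical weight. They do not change what the written steps compute, and recovering the direction does not tell anyone what *this result* means.

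A reader might infer that the plan would usually declare a false success, or that an effective device would usually fail. The documents do not support either. Each depends on one reading of the second condition and, for the whole procedure, on log-normal data. Beta-distributed ratios, which keep reductions between 0 and 100% and fit the documents equally well, give far smaller effects.

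A reader might also infer that the meaning would be settled after the results are known. That is not supported: section 10.2 promises a more detailed SAP, and the documents do not say when it will be written.

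Three qualifications remain. The impossibility under (a) holds for the unadjusted mean, and for site-adjusted means (section 10.7) if both quantities use the same site weights. With a median, success would be rare (about 0.1% in log-normal runs) rather than impossible. The percent change in section 10.4 is signed, so taken literally a negative change could satisfy none of the three readings; I have treated it as a reduction. Finally, n = 50 is the per-protocol target and the mITT set may be larger; log-normal runs at n = 60 with SD 16 and 20 showed the same pattern for (a) and (b).

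**Conclusion.** The fallback in item 1.a is wrong as written. It labels the upper limit of the reduction as a lower bound, and its second condition is undefined. The first fault is algebraic and holds for any data. The rates for the fallback alone (impossible, about 50%, or about 94–97% at a true mean reduction of 50%) assume n = 50 and SD 15–20.

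The effect on the trial as a whole is modest if the data are near normal or beta-shaped: false success of at most about 8% on the most lenient reading. It is large if they are log-normal: up to 48% false success under (c), or success at a true 60% reduction cut to 32–54% under (a). The documents do not say which shape to expect beyond hoping for normality. The t-test path is sound and unaffected.

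Because this is the decision rule for the primary endpoint and the repair is wording only, it should be corrected before the analysis.

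**What to change.** In section 10.6 item 1.a, keep the mean percent reduction of section 10.4 as the target. Suggested text: *If the normality check fails, the one-sided 98.33% lower t limit of the mean percent reduction remains the deciding analysis; the endpoint is met if it exceeds 50%.* The outcome of the normality check then no longer changes the decision.

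Also:

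- Report the log analysis as supportive, with the lower limit of the geometric-mean reduction given as 100 × (1 − exp(U)), where U is the upper one-sided 98.33% limit of mean ln(treatment/control).
- State how a woman with no treatment-phase pad weight gain enters the log step, since ln(0) is undefined.
- Delete the condition comparing the raw change with *this result*.
- Correct the pointer in section 10.4 from item 2 to item 1 of section 10.6.

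If the sponsor prefers the log rule to decide, the plan must say that the target is then the geometric-mean reduction, and that this rule rejects about 10–21% when the arithmetic-mean reduction is exactly 50%.

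The cost is wording in two sections, carried into the SAP, with no new data. The downside is slight size inflation, up to about 3% against 1.67%, if the data are skewed.
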